7.1.4. Subgroup analysis of the primary outcome

Assessment of the homogeneity of treatment effect by a subgroup variable will be conducted by a GLM with the treatment, subgroup variable, and their interaction term as predictors, and the *P*-value presented for the interaction term. In principle, there will be no adjustment for multiple comparisons for subgroup analyses and will be performed for the ITT. GLM model with binomial distribution and log link function will be used in subgroup analysis and derived RR and its 95%CI will be reported.

It should be aware that positive findings from these subgroup analyses have to be interpreted with caution since there is a non-negligible chance of false positives.

7.2. Secondary outcome Analysis

All secondary outcomes will be analyzed as a superiority design and two-sided 95% CIs for the treatment differences in these outcomes between two treatment groups will be calculated and presented. Secondary outcome analyses will be based on the ITT population unless specified.

7.2.1. Analysis of binary outcomes

Binary outcome with single measurement will be summarised by number (%) of participants with event by treatment group and analysed in a similar way as the primary endpoint by means of GLM model. The point estimate of RD and its two-sided 95% CI between high dose and low dose will be estimated. If RD cannot be estimated, RR will be estimated.

The secondary binary outcomes with repeated measurements at different time points will be summarized using number (%) of events at each time point and analyzed using a generalized estimating equation (GEE) model, in which treatment, time, interaction between treatment and time as fixed effects, HIE (presence or absence) and seizure burden (high or low) as covariates,

CONFIDENTIAL

and participant as cluster effect. Exchangeable covariance structure will be used. The RR together with their 95%CIs at each time point will be derived.

7.2.2. Analysis of continuous outcomes

The continuous variables such as biochemical markers will be summarised using number of subjects (n), mean, standard deviation (SD), median (IQR), minimum, and maximum by treatment group, and will be analysed by a GLM model with treatment as a study variable, HIE (presence or absence) and seizure burden (high or low) as covariates, and with normal distribution and identity link function. Differences in mean outcomes with their two-sided 95% CIs between two groups will be derived from the GLM model.

8. SAFETY ANALYSES

8.1. Adverse event

Safety analysis will be based on the safety population. Assessment of safety will be based on the incidence of treatment TEAE, TEAEs resulting in discontinuation, and serious TEAEs (SAEs). TEAE summaries will be provided showing the number and percentage of subjects who experienced at least 1 AE. These summaries will be presented by body system (system organ class) and preferred term (Medical Dictionary for Regulatory Activities). SAEs, TEAEs, ADRs, and SADRs resulting in discontinuation will be summarized separately.

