1.3 Schedule of Events

Study Procedure	Screening Period	Double-Blind Treatment Period	Follow-Up Period / Early Discontinuation/ End of Study
Study Day(s)	-1-0	0-1	1-2
NICU Admission	X		
Informed Consent	X		
Inclusion/Exclusion Criteria	X		
Delivery History	X		
Medical History	X		
Apgar Score	X		
Physical Examination (includes neurological exam)	X ¹		X ²
Height/Length (include Head Circumference and Abdominal Circumference)	X		
Body Weight	X		
Vital Signs ^{1,3}	X	X	X
Laboratory Safety Tests (Hematology, Chemistry, Coagulation) ^{1,4}	X	X	X
Continuous Video EEG Assessment ⁵	X	X	X
Clinical Seizure Assessment ⁶		X	X
Randomization		X	
Phenobarbital Administration		X	
Phenobarbital Maintenance Administration		X	X
Phenobarbital PK Samples ⁷		X	X
Recording of Additional Anticonvulsant Medication		X	
Prior and Concomitant Medication Review	X	X	X
Adverse Events Evaluation	X	X	X

Protocol
MI-5780

Version: 2.0; 07-Dec-2021

Phenobarbital Sodium Injection

Page 16 of 76

1. All neonates will undergo a baseline physical exam (including a neurologic exam), baseline vital signs (blood pressure, pulse rate, respiration rate, oxygen saturation, and auxiliary or rectal temperature) and baseline laboratory safety tests.
2. Physical examination and neurologic exam to be completed at end of Follow-up Period and/or prior to discharge.
3. Vital signs will be monitored and recorded prior to each (loading dose and second dose) phenobarbital treatment administration and every 15 ± 5 minutes up to 1 hour after the completion of each 30-minute dose infusion. Recording of vital signs will continue to be collected every 4-6 hours post phenobarbital administration through the Treatment Period and until completion of the Follow-up Period or at early study discontinuation. The 4-6 hours is calculated from initial loading dose start of infusion time.
4. Laboratory safety tests will be collected at the completion of the Treatment Period, at end of Follow-up Period and every 24 hours during the Open-Label Extension Period or at time of discharge/early study discontinuation.
5. cvEEG monitoring will be recorded for the study from time of informed consent or start of cvEEG (which ever comes last) and up to 48 hours after first loading dose of phenobarbital.

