3.1 Objectives

3.1.1 Primary Objective

The primary objective is to evaluate a potential dose-response of two different doses of intravenous phenobarbital for safety and efficacy in a neonatal population at high risk for seizures.

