If seizures persist (≥ 30 sec/h of seizure activity) 60 minutes following the start of the initial dose of phenobarbital, neonates receiving an initial dose of 20 mg/kg will receive an additional 20 mg/kg dose. Neonates receiving an initial dose of 40 mg/kg will receive an additional 10 mg/kg dose. Administration of this second loading dose is required to be within 2 hours of recognition of qualifying seizure burden (≥ 30 sec/h). The time period between the first and second dose of study treatment will be determined by the principal investigator or site designee (recommended to be a pediatric neurologist and/or neurophysiologist) review of the cvEEG, but must be at least 30 minutes after infusion is completed and no more than 24 hours after the first dose of study treatment (22).

If the seizure activity continues (≥ 30 sec/h) is still not resolved, study participants may receive a second-line alternative anticonvulsant therapy per institutional protocol. In each treatment arm, the second-line anticonvulsant therapy will be confirmed by the principal investigator or site designee (recommended to be a pediatric neurologist and/or neurophysiologist) and recorded in the study documentation as a concomitant medication.

All phenobarbital treatment doses will be prepared by the unblinded investigational pharmacist. The investigational pharmacist will be unblinded (have access to the treatment arm labels) and will not be involved in the assessment or medical management of the neonate. All other study personnel will be blinded to the first and second phenobarbital dose treatment. Each study treatment arm will be prepared in the same total volume of administration and administered over a **30-minute infusion** in order to maintain the study blind.

Throughout the Treatment Period the neonate will be continuously monitored by cvEEG, vital signs will be recorded, clinical seizure assessment will be recorded, and blood samples will be collected for laboratory safety monitoring and phenobarbital plasma concentrations according to the schedule of activities (Section 1.3). cvEEG monitoring will continue throughout the Treatment

Period and will be discontinued at end of Follow-up Period or upon entering Open Label Extension Period.

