8.3.4 Time Period and Frequency for Event Assessment and Follow-up

The occurrence of an adverse event (AE) or serious adverse event (SAE) may come to the attention of study personnel during study visits and interviews of a study participant presenting for medical care, or upon review by a study monitor.

All AEs including local and systemic reactions not meeting the criteria for SAEs will be captured on the appropriate case report form (CRF). Information to be collected includes event description, time of onset, clinician's assessment of severity, relationship to study product (assessed only by those with the training and authority to make a diagnosis), and time of resolution/stabilization of the event. All AEs occurring while on study must be documented appropriately regardless of relationship. All AEs will be followed to adequate resolution.

Any medical condition that is present at the time that the participant is screened will be considered as baseline and not reported as an AE. However, if the study participant's condition deteriorates at any time during the study, it will be recorded as an AE.

Changes in the severity of an AE will be documented to allow an assessment of the duration of the event at each level of severity to be performed. AEs characterized as intermittent require documentation of onset and duration of each episode.

PI will record all reportable events with start dates occurring any time after informed consent is obtained until 7 (for non-serious AEs) or 30 days (for SAEs) after the last day of study participation. A follow-up call at day 7 or day 30 will be conducted to confirm resolution or stabilization of adverse events. At each study visit, the investigator will inquire about the occurrence of AE/SAEs since the last visit. Events will be followed for outcome information until resolution or stabilization.

Any adverse event or abnormal laboratory result considered clinically relevant will be followed until it reaches a satisfactory resolution, becomes stable, or can be explained by other causes (e.g., concurrent condition or medication), and clinical judgment indicates that further evaluation is not warranted. All findings must be reported in the study participant's file.

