2.1. Primary Objective

To evaluate a potential dose-response of two different doses of intravenous phenobarbital for safety and efficacy in a neonatal population at high risk for seizures.

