3.6. Sample Size

Literature supports that lower loading doses of phenobarbital achieve seizure control in approximately 30 to 60% of treated neonates, with higher loading doses achieving seizure control up to 85%. Based on an effect size of 20% (from 50% in the low dose group to 70% in the high dose group), an alpha of 0.05 and 80% power, it is estimated that the number of completed subjects required will be 93 subjects in each group (total 186). With approximately, 5% dropout resulting in non-evaluable primary outcome, the minimum required for randomization will be 196.

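### The primary objective asks for a dose-response in safety, but the only planned adverse-event analysis is a whole-study count by arm, which compares the two regimens and cannot isolate 20 from 40 mg/kg

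*SAP*

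**What the plan says.** The primary objective in Protocol 3.1.1 is to "evaluate a potential dose-response of two different doses of intravenous phenobarbital for safety and efficacy", and SAP 2.1 repeats it. Efficacy is tied to the first dose: Protocol 9.1 frames the hypothesis around single-dose administration, and any additional seizure treatment within 24 hours counts as failure.

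Safety has no such anchor. SAP 8.1 says "TEAE summaries will be provided showing the number and percentage of subjects who experienced at least 1 AE", broken down by system organ class and preferred term, and Protocol 9.4.4 says the same. SAP 4.3 groups infants by randomised treatment unless the wrong treatment was given throughout. No section defines the treatment-emergent window.

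Treatment changes while events are being recorded. Under Protocol 4.1, if seizures persist, "neonates receiving an initial dose of 20 mg/kg will receive an additional 20 mg/kg dose"; the high-dose arm gets a further 10 mg/kg. Protocol 4.1 and 4.3 allow other anticonvulsants. Protocol 4.1.5 and 6.1.2 allow 5 mg/kg/day open-label phenobarbital for up to 72 hours in either arm, starting after the 24-hour Treatment Period. Recording of events continues through the extension (Protocol 1.3.1) and "until 7 (for non-serious AEs) or 30 days (for SAEs) after the last day of study participation" (Protocol 8.3.4).

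**The concern.** A dose-response question about safety needs at least one comparison in which the arms differ by the doses of interest. The trial randomises first doses of 20 and 40 mg/kg, but an infant counted as a low-dose case may have had the event after a total of 40 mg/kg, after a second-line drug, or during maintenance that is the same in both arms. A count of infants with at least one event over the whole study cannot tell these apart.

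The stake is interpretation. If the two arms show similar event rates, a reader could conclude that a 40 mg/kg loading dose is as safe as 20 mg/kg, when a substantial part of the low-dose arm also received 40 mg/kg. There is a further complication: at the planning rates the low-dose arm has more second infusions, and so more occasions on which an infusion-related event can be recorded. That could mask a difference at the first infusion.

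**Working it through.** **Inputs.** Planned control rates are "from 50% in the low dose group to 70% in the high dose group" (SAP 3.6). The cited range for lower doses is that they "achieve seizure control in approximately 30 to 60% of treated neonates", with up to 85% for higher doses (same section). Second doses are +20 mg/kg (low arm) and +10 mg/kg (high arm) (Protocol 4.1). Maintenance is 5 mg/kg/day for up to 72 hours (Protocol 4.1.5, 6.1.2).

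**The plan's own figure.** With two-sided alpha 0.05, 80% power and pooled variance without continuity correction:

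n = [1.96·√(2·0.6·0.4) + 0.842·√(0.5·0.5 + 0.7·0.3)]² / 0.20² = 93 per arm, 186 in all; 186/0.95 = 195.8, so 196 randomised.

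This matches the documents, so 50% and 70% are the working rates. They imply that 50% of the low arm and 30% of the high arm qualify for a second dose.

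**Number reaching a second dose, 98 per arm.** Low: 0.50 × 98 = 49, each reaching 40 mg/kg. High: 0.30 × 98 ≈ 29, each reaching 50 mg/kg.

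**Mean loading dose** = first dose + (proportion not controlled) × (second dose).

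- Low: 20 + 0.50 × 20 = 30 mg/kg.
- High: 40 + 0.30 × 10 = 43 mg/kg.
- Contrast: 13 mg/kg instead of 20 (35% lost, 65% kept); the ratio falls from 2.00 to 1.43.

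**Range.** The contrast is 20 + 10·f(high) − 20·f(low), where f is the proportion not controlled. The cited rates give f(low) of 40% to 70%. For f(high) I take 15% (from the cited 85%) to 30% (the planning value).

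- Largest: 20 + 3 − 8 = 15 mg/kg (25% lost).
- Smallest: 20 + 1.5 − 14 = 7.5 mg/kg (about 63% lost).

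**If some infants get another drug instead.** Assume that only 75% of non-responders in each arm receive the second dose. The share of the low arm reaching 40 mg/kg is then 37.5%, the means are 27.5 and 42.25 mg/kg, and the contrast is 14.75.

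**Open-label maintenance.** Three daily doses add 3 × 5 = 15 mg/kg. If every infant in both arms received this, the means would be 45 and 58 mg/kg: the contrast stays at 13 and the ratio falls to 1.29.

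**Illustration of the effect on detection.** The documents give no event rates, so assume that risk is proportional to cumulative dose, with 98 per arm.

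| Assumed risk at 20 mg/kg | First doses only | Power | Both loading doses | Power |
|---|---|---|---|---|
| 10% | 10% v 20% | 50% | 15.0% v 21.5% | 22% |
| 15% | 15% v 30% | 71% | 22.5% v 32.3% | 33% |

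This shows the direction and rough size of the dilution. It does not predict what a 60-minute table would detect.

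**Is there a window before any second dose?** T0 is the start of the first infusion (Protocol 3.2.1). The infusion lasts 30 minutes, and a second dose is barred until 30 minutes after it ends (Protocol 4.1, 6.1.2). The earliest second dose is therefore at T0 + 30 + 30 = T0+60 min. Event onset is collected (Protocol 8.3.5), and vital signs are taken "every 15 ± 5 minutes up to 1 hour after the completion of each 30-minute dose infusion" (Protocol 1.3, footnote 3), nominally at T0+45, +60, +75 and +90 min. SAP 8.2 summarises vital signs and their changes by treatment but names no time points.

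**The case against.** The strongest reply is that the randomised treatments are regimens. SAP 3.2 defines each treatment as a first dose with a conditional second dose, and Protocol 4.3 speaks of dose regimens. Needing the second dose is a consequence of the assigned first dose, so analysis by randomised arm is an unbiased comparison of the regimens. This stands. A reader might infer that the planned table is biased toward no difference. That does not follow for the regimen question. Dilution arises only when the table is read as 20 versus 40 mg/kg, and it points toward no difference only if risk rises with dose.

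Other limits also stand:

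- The SAP never states that it combines periods. That follows from its silence on window and period, and the 7- and 30-day limits govern recording, not a stated analysis window.
- The share reaching 40 mg/kg is inferred from a planning rate for seizure control; it is not a second-dose rate.
- The first 60 minutes should not be called uncontaminated. Protocol 4.1 and 4.3 let the investigator use another anticonvulsant at any time, so the window excludes only a second phenobarbital dose.
- The window is short, and half of it is the infusion. Protocol 2.3.1.4 lists drowsiness, lethargy and poor feeding, and ties respiratory depression, apnea and hypotension to over-rapid administration. With a half-life near 114 hours (Protocol 8.2.7.1), first-dose effects outlast an hour. A null result there would not show equal safety.

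There is partial mitigation: exposure is summarised by treatment (SAP 6.4), data listings carry time points (Protocol 9.4.8), and an unblinded DSMB reviews safety. None of these gives a between-arm adverse-event estimate for a defined period.

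**Conclusion.** The gap is real but limited. The planned adverse-event table validly compares 20+20 with 40+10 mg/kg. It does not isolate the first-dose contrast, and nothing in the SAP tells the reader so. At the planning rates the contrast in mean loading dose is 13 instead of 20 mg/kg, or 7.5 to 15 over the rates considered. About half the low-dose arm would reach 40 mg/kg (40% to 70% over the cited range; fewer where an alternate drug replaces the second dose).

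It would go too far to say that the exposure difference has largely closed. At the planning rates 65% of it remains, and maintenance does not reduce the absolute difference if uptake is equal in the two arms. All these figures assume that second-dose use follows the planned control rates, except where reduced use is stated. This is a worthwhile, inexpensive improvement to the safety analysis; it does not invalidate the comparison already planned.

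**What to change.** In SAP 8.1:

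1. Define a treatment-emergent adverse event and its window.
2. Make events with onset from T0 to 24 h, by randomised arm, with risk difference and 95% CI, the main regimen safety comparison.
3. Add a supportive first-dose table of events with onset from T0 to T0+60 min. State that this window is free of a second phenobarbital dose but not necessarily of other drugs, and that it misses later effects such as sedation and poor feeding.
4. Tabulate 24–48 h and open-label events separately. Maintenance can begin before 48 h (Protocol 1.3.1, footnote 4), so give a rule for events that fall in both.
5. Keep the whole-study table, labelled as a regimen comparison and not as 20 versus 40 mg/kg.
6. If any table is cut at the second dose, use person-time and label it non-randomised, because the cut depends on outcome and tends to come sooner in the low-dose arm.

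In SAP 8.2, add by-arm vital-sign changes at the post-infusion readings up to T0+60 min, and keep the later scheduled readings in the general summary.

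The cost is SAP wording and a few tables from data already collected. Counts in the 60-minute window will be small and the intervals wide. No treatment or procedure changes.

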8.2. Vital Signs

Vital sign data including blood pressure (BP), heart rate, respiratory rate and body temperature will be listed for individual subjects.

Vital sign data, along with changes from baseline will be summarized separately, overall and by treatment using descriptive statistics. For each vital sign variable, baseline value will be calculated as the last value prior to dosing.

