2.3.1.4 Adverse Reactions

Expected phenobarbital adverse reactions include drowsiness, lethargy, impaired sucking reflex and poor feeding. If administration is too rapid, expected adverse reactions include respiratory depression, apnea, hypotension, laryngospasm and bronchospasm. Other expected adverse reactions include phlebitis, tissue necrosis if extravasation occurs, GI intolerance, physical dependence and tolerance, folate deficiency, hepatitis and hypocalcaemia.

Stevens-Johnson syndrome and Toxic Epidermal Necrolysis: Serious and sometimes fatal dermatologic reactions, including Stevens-Johnson syndrome (SJS) and Toxic Epidermal Necrolysis (TEN) have been reported with phenobarbital. Post-marketing reporting rate is generally accepted to be an underestimate due to under-reporting. Recurrence of serious skin reactions following re- challenge with phenobarbital has also been reported. Therefore, if a study participant develops a skin reaction during phenobarbital treatment, consideration should be given to permanent discontinuation and replacement of the drug with alternative treatment.

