3.2.4 Safety Endpoints

The following safety assessments will be performed during the study:

- Type, incidence, and severity of adverse events
- Physical examination (including neurologic exam)
- Vital signs (blood pressure [arterial line], respiration rate, pulse rate, oxygen saturation, and temperature)
- Clinical laboratory tests (hematology, serum chemistry)

3.2.4.1 *Justification for Safety Endpoints*

Safety monitoring is a standard, yet critical component of any clinical trial. The safety assessments in this study are not beyond that of standard safety assessments performed in many clinical studies.

4 Study Design

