3.7.2. Secondary outcomes

Efficacy

- Percent of neonates who do not require additional seizure treatment after 2 hours of the first dose of phenobarbital.

CONFIDENTIAL

- Percent of neonates who do not require additional seizure treatment after the second dose of phenobarbital within the first 24 hours of treatment.
- Seizure burden over 24 hours following initial administration of the phenobarbital injection.
- Seizure burden over 48 hours following initial administration of the phenobarbital injection.
- Percent of neonates requiring alternative anticonvulsive therapy for the management of seizures at 24 and 48 hours.
- Time period between the first dose and second dose of intravenous phenobarbital in neonates randomized.
- Time period between the second dose of intravenous phenobarbital and alternative anticonvulsant treatment in neonates
- Time period between the first dose of intravenous phenobarbital and administration of an alternative anticonvulsant treatment in neonates randomized.

Safety

The following safety assessments will be performed during the study:

- Type, incidence, and severity of adverse events
- Physical examination
- Vital signs (blood pressure [arterial line], respiration rate, pulse rate, oxygen saturation and temperature)
- Clinical laboratory tests (hematology, serum chemistry)

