5.2. Data Summaries

Continuous variables will be summarised according to number of subjects with non-missing data (n), mean, standard deviation (SD), median, minimum, and maximum.

Categorical variables will be summarised according to the absolute frequency and percentage of subjects (%) in each category level. The denominator for the percentages is the number of subjects in the treatment arm with data available, unless noted otherwise.

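### SAP 8.2 does not name oxygen saturation, a listed safety endpoint, and prespecifies no between-arm summary of the readings taken soon after each infusion

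*SAP*

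**What the plan says.** Both documents define the safety vital signs with oxygen saturation among them. Protocol 3.2.4 has "Vital signs (blood pressure [arterial line], respiration rate, pulse rate, oxygen saturation, and temperature" and SAP 3.7.2 has "Vital signs (blood pressure [arterial line], respiration rate, pulse rate, oxygen saturation and temperature". Protocol 1.3 (footnote 1) and 8.2.6 also have it recorded.

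SAP 8.2, the only SAP section on how vital signs are analysed, has two operative sentences:

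- on listings: "Vital sign data including blood pressure (BP), heart rate, respiratory rate and body temperature will be listed for individual subjects"
- on summaries: "Vital sign data, along with changes from baseline will be summarized separately, overall and by treatment using descriptive statistics"

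It adds that baseline is the last value before dosing. SAP 5.2 says what descriptive statistics means here: "Continuous variables will be summarised according to number of subjects with non-missing data (n), mean, standard deviation (SD), median, minimum, and maximum".

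Protocol 1.3 sets two collection schedules. The dense one runs "every 15 ± 5 minutes up to 1 hour after the completion of each 30-minute dose infusion", after a reading before each dose. The sparse one follows: "Recording of vital signs will continue to be collected every 4-6 hours post phenobarbital administration through the Treatment Period", and on to the end of the Follow-up Period.

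Protocol 2.3.1.4 says that, if administration is too rapid, "expected adverse reactions include respiratory depression, apnea, hypotension, laryngospasm and bronchospasm".

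**The concern.** Oxygen saturation is the one vital sign in SAP 3.7.2 that SAP 8.2 does not name, and it is among the measures closest to the respiratory risks in Protocol 2.3.1.4. A programmer building tables from 8.2 is not told to include it.

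The second gap is time. The two first doses are infused over the same 30 minutes, so the rate is 40/30 = 1.33 mg/kg per minute in one arm and 20/30 = 0.67 in the other. The protocol links respiratory depression, apnea and hypotension to speed of administration, so the period just after the first infusion is where a dose difference in these effects would most plausibly appear. The protocol collects dense readings there, but the SAP plans no table that uses them as such.

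Safety dose-response is part of the primary objective (Protocol 3.1.1, SAP 2.1). At stake is whether the trial can report, from systematic data and by a rule fixed in advance, how often infants in each arm had an acute respiratory or haemodynamic change. Cut-offs chosen after unblinding would carry little weight.

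**Working it through.** **1. Text comparison.**

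| Item | Endpoint lists (Protocol 3.2.4, SAP 3.7.2) | SAP 8.2 |
|---|---|---|
| Blood pressure | named | named |
| Pulse / heart rate | named | named |
| Respiratory rate | named | named |
| Temperature | named | named |
| Oxygen saturation | named | not named |
| Time points | dense and sparse schedules in Protocol 1.3 | none stated |
| Post-dose window, worst value, percent abnormal | – | none stated |

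SAP 8.3 at least defines laboratory change at each assessment; 8.2 has no equivalent. Protocol 9.4.4 again offers only descriptive statistics and changes from baseline.

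**2. Arm size.** The only plan figure needed is the sample size. For 50% v 70%, two-sided alpha 0.05, 80% power, pooled variance and no continuity correction, n = 93 per group, as stated. Allowing for 5% dropout, 186/0.95 = 195.8, so 196 randomised, or 98 per arm.

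**3. What an arm minimum can show.** The event rates here are assumptions; the documents give none. The chance that an arm of 98 contains at least one affected infant is 1 − (1 − p)^98.

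- p = 5%: 1 − 0.95^98 = 99.3%
- p = 20%: over 99.9%

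With a fourfold difference in risk, both arms would almost surely contain an affected infant. The minimum shows that an event occurred and how deep it was, not how many infants had one (expected 98 × 0.05 = 4.9 v 98 × 0.20 = 19.6).

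**4. What a yes/no comparison could show.** Power = Φ{[d√n − 1.96√(2m(1 − m))] / √(p1(1 − p1) + p2(1 − p2))}, with d = p2 − p1, m = (p1 + p2)/2 and n = 98. The 95% half-width is 1.96√[(p1(1 − p1) + p2(1 − p2))/98].

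| Assumed rates | Numerator / denominator | Power | Difference ± half-width |
|---|---|---|---|
| 5% v 10% | (0.495 − 0.730)/0.371 = −0.63 | 26% | 5 ± 7.3 points |
| 5% v 15% | (0.990 − 0.832)/0.418 = 0.38 | 65% | 10 ± 8.3 points |
| 5% v 20% | (1.485 − 0.917)/0.456 = 1.25 | 89% | 15 ± 9.0 points |

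**5. Length of the window.** Dense readings after the first dose end at 30 + 60 = 90 minutes from T0. Protocol 4.1 allows the second dose from 30 minutes after the first infusion ends, that is T0 + 60 minutes. A fixed T0–90 minute window could therefore include part of a second infusion, which is 20 mg/kg in one arm and 10 mg/kg in the other and goes only to infants still seizing. The window has to close at the second dose.

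**The case against.** The case for leaving the text alone has real force.

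- **The vital-sign list is open.** It follows the word including and governs individual listings. The summary sentence covers vital sign data without restriction, and SAP 3.7.2 keeps oxygen saturation as an endpoint. This stands: a reader might infer that the endpoint has been dropped, and the documents do not support that. It is left unnamed in the section that should specify its analysis.
- **The summaries are broader than mean changes.** A reader might infer that vital signs are reported only as overall mean changes. SAP 8.2 covers values and changes, overall and by treatment, and SAP 5.2 adds median, minimum and maximum.
- **Pooling is not stated.** A reader might infer that the 15-minute readings will be averaged with the 4–6-hourly ones to 48 hours, diluting an early effect. SAP 8.2 is silent on time points, and silence is not a pooling rule.
- **Other safeguards exist.** Protocol 9.4.8 requires listings sorted by treatment, participant and time point. SAP 8.1 tabulates treatment-emergent adverse events by preferred term. The DSMB reviews data after 10% and 50% of randomised participants. It would be wrong to say that acute respiratory depression would go unseen.
- **The risk statement is conditional.** Protocol 2.3.1.4 ties these reactions to administration that is too rapid, and the documents do not state the purpose of the 15-minute schedule.

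None of this supplies the missing display. Listings give no between-arm estimate. Adverse event counts depend on what investigators judge and report, whereas the scheduled readings do not. Arm minima carry no frequency (step 3).

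**Conclusion.** The point holds as an omission and an under-specified safety analysis. SAP 8.2 does not name a listed safety endpoint, and it prespecifies no time-point, post-dose-window, worst-value or incidence summary of readings that the protocol already collects. The consequence is that no planned between-arm comparison gives the frequency of acute respiratory or haemodynamic events from the systematic readings.

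The weight is modest: a cheap improvement that does not touch the primary analysis or the sample size. The event rates in steps 3 and 4 are illustrative. Across the assumed range, power runs from 26% to 89%, so the added comparison should be read as descriptive, through its interval, and a null result would not exclude a small difference.

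**What to change.** In SAP 8.2:

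1. Name oxygen saturation with the other four vital signs.
2. Summarise each vital sign by arm at each scheduled time point, as values and as change from baseline.
3. For oxygen saturation, respiratory rate, heart rate and blood pressure, report by arm the worst value from T0 to the earlier of 90 minutes or the start of a second dose.
4. For the same window, report by arm the percent of infants crossing analysis limits, with a 95% CI for the difference. The sponsor should set these limits before unblinding. They serve analysis only and imply no clinical rule.
5. Show readings after the second dose separately.

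The cost is SAP wording and a few tables; all the data are already scheduled. One limitation should be stated with the table: infants given an early second dose have a shorter window, down to 60 minutes, and that may differ by arm. Report how many windows were cut short in each arm.
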